12.2.4 Populations Used in Analyses

The primary immunogenicity analyses will be performed on the PPAS, including the PPAS1 and PPAS2. Additional immunogenicity analyses will be performed on the FAS for exploratory purposes, including FAS1 and FAS2, according to randomization group. The safety analysis will be performed on the SafAS (SafAS, and SafAS1 through SafAS4).

12.3 Handling of Missing Data and Outliers

12.3.1 Safety

No replacement will be done.

12.3.2 Immunogenicity

Missing data will not be imputed. No test or search for outliers will be performed.

12.4 Interim Analysis

No interim analyses are planned.

12.5 Determination of Sample Size and Power Calculation

Approximately 870 subjects will be enrolled in Group 1 and Group 2. An estimated around 20% to 30% and not higher than 40% of non-evaluable subjects will result in at least 522 subjects in the Per-Protocol population available for immunogenicity analyses. Group 1 will have 435 enrolled subjects and 261 evaluable subjects. Group 2 will have 435 enrolled subjects and 261 evaluable subjects. In addition, 200 subjects will be enrolled in Group 3 and Group 4.

In case of unexpected situations or any study hold resulting in an unexpected number of unevaluable subjects, total sample size may be increased to replace withdrawn, or unevaluable subjects.

For the Primary Objective:

Thirty days after the month 12 vaccination (after the second dose vaccination)

With at least 261 evaluable subjects in Group 1 and at least 261 evaluable subjects in Group 2, the study will have around 90.0% power by using Farrington and Manning's method to declare the non-inferiority of Group 1 vs Group 2.

Table 12.1: Power estimates to reject primary null hypothesis

Antigen	Endpoint	Estimated response (%)*	Non-inferiority margin	Power (%)
A	Seroresponse Rate	97.7	10%	100
C	Seroresponse Rate	97.8	10%	100
Y	Seroresponse Rate	93.3	10%	99.0
W	Seroresponse Rate	86.7	10%	91.0
Overall				90.0

Note: Evaluable subjects: Group 1 = 261 subjects; Group 2 = 261 subjects

*Estimated responses are based on results observed in MET39

For Secondary Objective 1:

Thirty days after the month 12 vaccination (after the second dose vaccination)

With 261 evaluable subjects in Group 1 and 261 evaluable subjects in Group 2, the study will have 100% power by using Farrington and Manning's method to declare the non-inferiority of Group 1 vs Group 2.

Table 12.2: Power estimates to reject the secondary null hypothesis

Antigen	Endpoint	Estimated response (%)*	Non-inferiority margin	Power (%)
A	% \geq 1:8	>99.9	10%	100
C	% \geq 1:8	>99.9	10%	100
Y	% \geq 1:8	97.8	10%	100

W	% ≥1:8	97.8	10%	100
Overall				100

Note: Evaluable subjects: Group 1 = 261 subjects; Group 2 = 261 subjects

*Estimated responses are based on results observed in MET39

13 Ethical and Legal Issues and Investigator / Sponsor Responsibilities

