6.5 Randomization and Allocation Procedures

On the day of enrollment, subjects who meet the inclusion/exclusion criteria and whose parent / guardian signs the ICF will be randomly assigned to either Groups 1, 2 or Groups 3, 4 in a 1:1 ratio depending on the age at recruitment. Approximately 870 healthy infants 6 to 7 months of age will be randomized 1:1 to either Group 1 or Group 2, and 200 healthy toddlers 17 to 19 months of age will be randomized 1:1 to either Group 3 or Group 4.

Site staff will connect to the IRT system, enter the identification and security information, and confirm a minimal amount of data in response to IRT system prompts. The IRT system will then provide the group assignment and have the site staff confirm it. The full detailed procedures for group allocation are described in the Operating Guidelines. If the subject is not eligible to participate in the study, then the information will only be recorded on the subject recruitment log.

Subject numbers that are assigned by the IRT system will consist of a 12-digit string (a 3-digit country identifier, a 4-digit study center identifier, and a 5-digit subject identifier). For example, Subject 840000100005 is the fifth subject enrolled in Center Number 1 in the US (840 being the US country code).

Subject numbers should not be reassigned for any reason. The randomization codes will be kept securely in the IRT system.

^a All unexpected and related SAEs submitted to European Union competent authorities must be unblinded.

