12.1 Statistical Methods

Clinical data will be analyzed under the responsibility of the Biostatistics Platform of the Sponsor.

A statistical analysis plan (SAP) will be written and peer reviewed before any analyses. In accordance with the protocol, the SAP will describe all analyses to be performed under the responsibility of the Sponsor and all the conventions to be taken.

Multiplicity adjustment is not required. Testing of the secondary hypotheses is dependent on successful rejection of the primary hypotheses. Within primary and secondary hypotheses, the intersection-union testing procedure (58) is being applied.

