12.1.3.1 Hypotheses

Thirty days after receiving MenACYW conjugate vaccine at 12 months of age, the percentage of subjects that achieve hSBA titers $\geq 1:8$ for meningococcal serogroups A, C, Y, and W in Group 1 are non-inferior to the corresponding percentages in Group 2.

Null hypothesis (H0): $p(\text{men, G1}) - p(\text{men, G2}) \leq -10\%$

Alternative hypothesis (H1): $p(\text{men, G1}) - p(\text{men, G2}) > -10\%$

where $p(\text{men, G1})$ and $p(\text{men, G2})$ are the percentages of subjects who achieve hSBA $\geq 1:8$ in Group 1 and Group 2 respectively. Each of the serogroups A, C, Y, and W will be tested separately. Assuming the difference between the 2 proportions is normally distributed, if the lower limit of the 2-sided 95% CI of the difference between the 2 proportions is $> -10\%$, the inferiority assumption will be rejected.

For the non-inferiority hypotheses using the seroprotection rates, the CI of the difference in proportions is computed using the Wilson Score method without continuity correction.

In general, categorical variables will be summarized and presented by frequency counts, proportion percentages and CIs. The 95% CIs of point estimates will be calculated using the normal approximation for quantitative data and the exact binomial distribution (Clopper-Pearson method) for proportions. For GMTs and GMCs, 95% CIs of point estimates will be calculated using normal approximation assuming they are log-normally distributed.

For secondary objectives 2, 3, 4, and 5, no hypothesis will be tested, and descriptive statistics will be used.

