5.1.2 Hypotheses and Statistical Methods for Secondary Objective(s)

5.1.2.1 Hypotheses for secondary objective 1

Thirty days after receiving MenACYW conjugate vaccine at 12 months of age, the percentage of subjects that achieve hSBA titers $\geq 1:8$ for meningococcal serogroups A, C, Y, and W in Group 1 are non-inferior to the corresponding percentages in Group 2.

Null hypothesis (H0): $p_{(\text{men, G1})} - p_{(\text{men, G2})} \leq -10\%$

Alternative hypothesis (H1): $p_{(\text{men, G1})} - p_{(\text{men, G2})} > -10\%$,

where $p_{(\text{men, G1})}$ and $p_{(\text{men, G2})}$ are the percentages of subjects who achieve hSBA $\geq 1:8$ in Group 1 and Group 2 respectively.

5.1.2.2 Statistical Methods for secondary objective 1

Each of the serogroups A, C, Y, and W will be tested separately. If the lower limit of the 2-sided 95% CI of the difference between the 2 proportions is $> -10\%$, the inferiority assumption will be rejected.

For the non-inferiority hypotheses using the seroprotection rates, the CI of the difference in proportions is computed using the Wilson Score method without continuity correction in [Section 5.1.1.2](#).

The overall non-inferiority of this objective will be demonstrated if all 4 individual null hypotheses are rejected.

5.1.2.3 Statistical Methods for secondary objectives 2, 3, 4 and 5

No hypotheses will be tested. Descriptive statistics will be presented. The statistics presented on [Table 5.1](#) will be produced as applicable. The 95% CIs of point estimates will be calculated using the exact binomial distribution (Clopper-Pearson method) for proportions (1). For GMs, 95% CIs of point estimates will be calculated using normal approximation assuming they are log-normally distributed.

Descriptive statistics listed below will be provided for the immunogenicity endpoints in [Section 4.2.2.1](#).

Table 5.2: Statistical analyses for immunogenicity objective(s)

Objectives	Group	Time point	description
Primary (hypothesis testing)	Group 1 and 2	D30 after 2 nd vaccination	Vaccine seroresponse rate 30 days after 2 nd vaccination
Secondary (hypothesis testing)	Group 1 and 2	D30 after 2 nd vaccination	Seroprotection (titers $\geq 1:8$) 30 days after 2 nd vaccination
	Group 1 and 2	D0 (all subjects)	hSBA GMT and 95% CI
		D30 after 1 st vaccination (50% subjects)	hSBA titer distribution and RCDC

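### The 100% power stated for declaring non-inferiority on secondary objective 1 leaves out the plan's own testing order; with 261 evaluable per group the figure is about 90%

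*Protocol*

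**What the plan says.** **Testing order.** Protocol 12.1 states: "Testing of the secondary hypotheses is dependent on successful rejection of the primary hypotheses". The next sentence sets the rule inside each family: "Within primary and secondary hypotheses, the intersection-union testing procedure (58) is being applied". SAP 5.1.2 spells this out for secondary objective 1: "The overall non-inferiority of this objective will be demonstrated if all 4 individual null hypotheses are rejected". SAP 5.1.1.2 has the same all-four rule for the primary objective. SAP 5.1.2 and SAP 5.5 do not repeat that the secondary tests depend on the primary.

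**Test for each serogroup.** Protocol 12.1.3.1 rejects inferiority "if the lower limit of the 2-sided 95% CI of the difference between the 2 proportions" lies above -10%. The interval is the Wilson score interval without continuity correction.

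**Power statements.** Protocol 12.5 gives both objectives for the same numbers: "Evaluable subjects: Group 1 = 261 subjects; Group 2 = 261 subjects". For the primary objective, Table 12.1 lists power of 100 (A), 100 (C), 99.0 (Y) and 91.0 (W), and 90.0 overall. For secondary objective 1 the text says "the study will have 100% power by using Farrington and" Manning's method to declare non-inferiority, and Table 12.2 shows 100 for each serogroup and 100 overall. Synopsis Tables S1 and S2 and SAP Tables 5.3 and 5.4 repeat these figures. None of these places says that the 100% ignores the testing order.

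**Where 261 comes from.** Protocol 12.5: "An estimated around 20% to 30% and not higher than 40% of non-evaluable subjects will result in at least 522 subjects". That is the worst case allowed for, not the expected one.

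**The concern.** Under Protocol 12.1, declaring secondary objective 1 requires eight rejections: four on seroresponse, then four on titer at or above 1:8. The stated 100% counts only the last four, yet the sentence describes what the study can declare and the table row is labelled as overall.

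Secondary objective 1 is the only tested claim besides the primary; Protocol 12.1.3.1 makes secondary objectives 2 to 5 descriptive. A reader who takes the 100% at face value will think this claim carries no risk under the planning assumptions. In fact it carries the whole risk of the primary, nearly all of it from the serogroup W seroresponse test. A reader of the SAP alone is worse placed, because the sections on this objective and on sample size do not mention the dependence.

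**Working it through.** **Inputs**
- n = 261 evaluable per group (Protocol 12.5), allocation 1:1 (Protocol 6.5: "Approximately 870 healthy infants 6 to 7 months of age will be randomized 1:1 to either Group 1 or Group 2").
- Margin 10 points; the lower limit of a two-sided 95% interval is used, so one-sided alpha is 0.025 and z = 1.96.
- Seroresponse rates (Table 12.1): A 97.7%, C 97.8%, Y 93.3%, W 86.7%.
- Titer rates (Table 12.2): A and C above 99.9% (99.9% used), Y and W 97.8%.
- The tables give one rate per serogroup, so the true rates are taken as equal in the two groups.

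**Step 1. Reproduce the primary power.** Farrington-Manning:

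power = Φ[(0.10 − 1.96·SE0) / SE1]

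SE1 = √(2p(1−p)/n). SE0 uses the rates fitted under a true difference of exactly −10 points.

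| Serogroup | p | Fitted rates under the null | SE0 | SE1 | Power |
|---|---|---|---|---|---|
| W | 0.867 | 0.8027, 0.9027 | 0.03072 | 0.02973 | Φ(1.339) = 91.0% |
| Y | 0.933 | 0.8579, 0.9579 | 0.02494 | 0.02189 | Φ(2.336) = 99.0% |
| A | 0.977 | 0.8878, 0.9878 | 0.02068 | 0.01312 | Φ(4.531) = 100.0% |
| C | 0.978 | 0.8884, 0.9884 | 0.02059 | 0.01284 | Φ(4.645) = 100.0% |

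The product over serogroups is 0.99025 × 0.90969 = 0.9008, against a stated 90.0%. Table 12.1 reproduces.

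**Step 2. Reproduce the secondary power, taken alone.** At p = 0.978 the power is Φ(4.645) = 99.9998%. At p = 0.999 it is 100.0%. The product over the four serogroups exceeds 99.99%, against a stated 100%. Table 12.2 reproduces as the power of these tests alone.

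**Step 3. Apply the testing order.** Let P1 be the probability that all four primary nulls are rejected and P2 the probability that all four secondary nulls would be rejected if tested. The probability of declaring secondary objective 1 lies between P1 + P2 − 1 and min(P1, P2), whatever the correlation between the two families. P2 is practically 1, so both bounds equal P1 to two decimals: 90.08%. On the plan's rounded figures the sum is 1.00 × 1.00 × 0.99 × 0.91 × 1.00 = 90.1%.

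**Step 4. Check against the planned interval.** Exact binomial enumeration of the Wilson score rule in SAP 5.1.1.2 gives W 91.6%, Y 99.3%, and A and C 100.0%. The primary overall is 0.99255 × 0.91590 = 90.9%. The secondary tests alone stay at 100%. Overall power for secondary objective 1 is then 90.9%.

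**Step 5. Allow dependence between serogroups.** Steps 1 to 4 multiply across serogroups, as the plan's overall figure does. Without assuming independence:
- Farrington-Manning: from 0.99025 + 0.90969 − 1 = 90.0% up to 91.0% (W alone).
- Exact: from 0.99255 + 0.91590 − 1 = 90.8% up to 91.6%.

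**Step 6. Expected evaluability.** At 40% non-evaluable, 870 × 0.6 / 2 = 261 per group. At 30%, 870 × 0.7 / 2 = 304.5, taken as 304. At 20%, 870 × 0.8 / 2 = 348.

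| Evaluable per group | Overall power, Farrington-Manning | Overall power, exact |
|---|---|---|
| 261 | 90.1% | 90.9% |
| 304 | 94.3% | 94.8% |
| 348 | 96.7% | 97.0% |

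**The case against.** The best defence is that nothing is miscalculated. Every entry in Tables 12.1 and 12.2 reproduces. Table 12.2 is titled as power to reject the secondary null hypothesis, and reporting each objective's power separately is common practice for an ordered endpoint. The order is stated openly in Protocol 12.1, and the primary's 90.0% stands directly above the secondary table, so a reader of the protocol can combine the two.

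Most of this stands: the fault is in what the 100% is said to describe, not in its computation. It does not rescue the sentence itself, which speaks of what the study will declare, nor the row labelled as overall. A serogroup-by-serogroup reading of the order would not help either, because success on all four secondary tests would still need all four primary tests.

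Three stronger readings are tempting, and the documents do not support them:
- *The secondary objective fails one time in ten whenever the planning assumptions are true.* That holds only at the floor of 261 per group. The plan expects 20% to 30% non-evaluable, where the failure rate is about 3% to 6%.
- *The statement hides an extra sensitivity to the W rate.* A W seroresponse below 86.7% would lower the primary's power, and the secondary would follow. That is a question about the primary's planning assumption, not a second fault here.
- *The trial is too small for this objective.* The primary drives the sample size, and its stated power is correct.

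**Conclusion.** The point holds as a misstatement of what the 100% covers. With 261 evaluable subjects per group, the design as ordered gives about 90% power to declare secondary objective 1, so the stated figure is 9 to 10 points too high for that event. At the expected evaluability the gap is about 3 to 6 points.

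This rests on the plan's own rates, equal true rates in the two groups and, for the product figures, independence between serogroups; dropping independence moves the result by no more than about one point. It also rests on reading Protocol 12.1 literally, as making every secondary test conditional on the primary. The trial's validity, error control and size are not affected. The correction is worth making because it concerns the only other tested claim and appears in both governing documents.

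**What to change.** In Protocol 12.5 with Table 12.2, in synopsis Table S2 and the sentence above it, and in SAP 5.5 with Table 5.4:
- Relabel the 100% as *power of the secondary tests alone, conditional on meeting the primary objective*.
- Add: *Because testing depends on success of the primary objective (Protocol Section 12.1), the overall power to declare secondary objective 1 with 261 evaluable subjects per group is about 90%.* The reference must name the protocol, since the SAP has no Section 12.1.
- Optionally add that the figure is about 94% to 97% at 30% to 20% non-evaluable.

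In SAP 5.1.2, state that secondary objective 1 is tested only if all four primary null hypotheses are rejected.

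The cost is a few sentences and table labels. No further subjects are needed and no alpha, margin or analysis changes. The only downside is a less favourable stated figure.

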13.1 Ethical Conduct of the Study / Good Clinical Practice

The conduct of this study will be consistent with the standards established by the Declaration of Helsinki and compliant with the ICH guidelines for GCP as well as with all local and / or national regulations and directives.

13.2 Source Data and Source Documents

“Source data” are the data contained in source documents. Source documents are original documents or certified copies, and include, but are not limited to, diary cards, medical and hospital records, screening logs, informed consent / assent forms, telephone contact logs, and worksheets. The purpose of study source documents is to document the existence of subjects and to substantiate the integrity of the study data collected. Investigators must maintain source documents so that they are accurate, complete, legible, and up to date.

For missing or discrepant data on a diary card, the study coordinator will obtain verbal clarification from the subject, enter the response into the “investigator’s comment” page of the diary card, and transfer the information to the CRB.

The subject pre-screening log should list all individuals contacted by the Investigators to participate in the study, regardless of the outcome.

The Investigator must print^a any electronic records on an ongoing basis, sign and date them immediately after creation, and keep the printouts on file as source documents that can be verified by the Sponsor or an inspector against the electronic records. Any subsequent changes of an electronic record require the record to be re-printed, dated (with an indication of the date of change), and signed. Such records must also be kept together with the original printed copy.

Good Documentation Practice should be followed by the Investigator and the site staff managing source documents.

13.3 Confidentiality of Data and Access to Subject Records

Prior to initiation of the study, the Investigator will sign a fully executed confidentiality agreement with Sanofi Pasteur.

^a Unless the electronic medical records are managed by validated computerized systems that are compliant with US 21 CFR Part 11, in which case they are acceptable on their own.

Sanofi Pasteur personnel (or designates), the IECs / IRBs, and regulatory agencies, including the FDA, require direct access to all study records, and will treat these documents in a confidential manner.

In the event a subject's medical records are not at the investigational site, it is the responsibility of the investigator to obtain those records if needed.

13.4 Monitoring, Auditing, and Archiving

13.4.1 Monitoring

Before the start of the study (i.e., before the inclusion of the first subject in the first center) the Investigators and the Sponsor's staff or a representative will meet at the site-initiation visit to discuss the study protocol and the detailed study procedures. Emphasis will be placed on inclusion and exclusion criteria, visit timing, safety procedures, informed consent procedures, SAE reporting procedures, CRB completion, and the handling of samples and products. The Sponsor's staff or a representative will ensure and document that all material to be used during the study has been received at the site; and that the study investigator team and local Sponsor/delegate staff have been properly informed about the study, GCP and regulatory requirements, and the Sponsor's procedures. The trial will follow a Risk Based Monitoring (RBM) strategy in which site generated data will be source reviewed and verified through a combination of on-site monitoring visits and centralized monitoring. Specific training sessions for the study investigator team and the CRAs on these topics may be performed as necessary, and should be documented.

The following instruction manuals will be provided: the CRB Completion Instructions for entering data into the CRB, and the Operating Guidelines for detailed study procedures such as the product management and sample-handling procedures.

After the start of the study, the Sponsor's staff or a representative will be in regular contact with the investigational team through telephone calls and regular follow-up visits. The Investigator or delegate must be available for these visits, and must allow the Sponsor/delegate staff direct access to subject medical files and CRBs. During these visits, the Sponsor/delegate staff will:

- Evaluate the quality of the study progress (adherence to protocol and any study-specific guidelines, quality of data collection and document completion, signature of consent forms, occurrence of SAEs, sample and product management, cold-chain monitoring, archiving)
- Source-verify completed CRBs and any corresponding answered queries.
- Determine the number of complete or ongoing issues identified at monitoring visits (e.g., protocol deviations, SAEs). Any identified problems will be discussed with the Investigator, and corrective or preventive actions will be determined, as appropriate.
- After all protocol procedures have been completed and the data have been entered into the CRB, the Investigator must still be available to answer any queries forwarded by the Sponsor. All data-related queries must be completed prior to database lock.

At the end of the study, a close-out visit will be performed to ensure that:

- The center has all the documents necessary for archiving.
- All samples have been shipped to the appropriate laboratories.
- All unused materials and products have been either destroyed or returned to the Sponsor.

13.4.2 Audits and Inspections

A quality assurance audit may be performed at any time by the Sponsor's Clinical Quality Assessment department (CQA) or by independent auditors to verify that the study has been conducted according to the protocol, GCP and ICH requirements, and other applicable regulations. An inspection may be conducted by regulatory authorities. The Investigator must allow direct access to study documents during these inspections and audits.

